### **Clinical Trial Monitoring**

Study monitoring visits may be postponed; however, the site monitor will continue to employ off-site monitoring practices such as routine communication methods (e.g., phone calls, emails, video visits) with the sites to get information on study progress, patient

Study Number: INVEX-CLIN-IIH-301 Protocol	Compound No.: Presendin
	Version: 5.0 for EU countries dated 08Dec2022

status, and information on issue resolution as detailed in the Data Monitoring Guidelines, Remote source data verification.

If the trial site monitor cannot be on-site to carry out the final drug accountability for reconciliation purposes, and the operation cannot be postponed, it may be carried out by a pharmacist from the site pharmacy or by the study coordinator/data manager with suitable training. The study drug can be returned to the sponsor by the site pharmacy directly, or destroyed in accordance with local practices, if applicable, and with sponsor approval.

### **Direct Contracts with Third Parties/Specialized Service Companies**

If necessary, direct contracts can be established with third-party local physicians to conduct activities related to the clinical management of patient for whom the investigator is responsible and maintains oversight. In such situations, the investigator is required to provide the local physician with a delegation letter listing all delegated activities. The sponsor, through the study investigator or institution, will reimburse the local physician for the test/procedures conducted outside of the standard of care.

Clinic visits should take place to the extent possible and usual protocol requirements adopted for all subjects as soon as the crisis-related limitations permit.

All safety data that are possible to obtain locally should be collected at a remote visit. These measurements may include the use of local practitioners and resources.

Exceptional measures taken in response to a crisis (e.g., COVID-19) and their impact on study results, such as tests done in a local laboratory, will be explained, assessed and reported in the clinical study report following ICH E3 guidance.

## **8. LIFESTYLE AND/OR DIETARY RESTRICTIONS**

Patients will receive lifestyle advice as per routine care from their treating physician.

## **9. INVESTIGATIONAL PRODUCT**

### **9.1. Dosage and Administration**

#### **9.1.1. Randomised Period**

During the 24-week randomised treatment period ([Figure 1](#)) patients will be randomised in a 1:1 ratio to receive active treatment or placebo.

Either

Study Number: INVEX-CLIN-IIH-301 Protocol	Compound No.: Presendin
	Version: 5.0 for EU countries dated 08Dec2022

Presendin (2.0mg exenatide) as a SC injection, self-administered once weekly.

Presendin is supplied as 2 parts, one vial consisting of a drug part (white or grayish white powder in a clear vial) and one pre-filled syringe containing the diluent part (colourless liquid). The drug part is suspended in the diluent part solution and administered as a suspension.

or

Placebo as a SC injection, self-administered once weekly.

Placebo is supplied as 2 parts (visually identical to the Presendin vial and pre-filled diluent syringe). The drug part will exclude the active pharmaceutical ingredient (exenatide acetate) and the diluent part will be the same as the active treatment diluent. The drug part is suspended in the diluent part solution and administered as a suspension.

## 9.2. Dose Rationale

The proposed 2mg weekly dose was based on the pharmacokinetic performance of the Peptron formulation (PT320). Pharmacokinetic profiles obtained after repeated once weekly dosing of 2mg of PT320 s.c. (as specified in the Presendin IB phase 2 clinical study in patients with type 2 diabetes) were comparable to those predicted by the population PK model developed for weekly s.c. administration of the recommended dose of the 2mg Bydureon extended-release formulation [Cirincione 2017], with time to reach the steady state slightly shorter for PT320 than for Bydureon (7-8 weeks vs 8-10 weeks) and with steady state plasma concentrations remaining within a comparable range for both products. Based on the same molecule and dose, comparable plasma concentrations for PT320 and Bydureon and the established safety profile of Bydureon a similarly acceptable safety and tolerability profile for PT320 is expected.

## 9.3. Maintaining the Blind

This is a double-blind trial.

A computer/website system will be used to maintain the blind for this trial. The site will be provided with website login details for the system. If the Investigator needs to unblind a patient's treatment, due to a medical emergency, the website should be accessed to unblind for that patient. .

The responsibility to break the treatment code in emergency situations resides solely with the investigator.

Study Number: INVEX-CLIN-IIH-301 Protocol	Compound No.: Presendin
	Version: 5.0 for EU countries dated 08Dec2022

#### **9.4. Treatment Assignment**

Patients will be randomised in a ratio of 1:1 to receive active treatment (Presendin) or placebo. A computer/website system will be used to randomly assign each patient to a treatment arm.

#### **9.5. Packaging and Labelling**

Individual supplies of trial medication will be provided to the sites in a double-blind format. The labels will contain all information required to meet the applicable local regulatory requirements.

Further information on packaging, labelling and dispensing are included in the Pharmacy Manual.

#### **9.6. Preparation**

Each dose of trial medication is provided as two parts, a single use vial and a pre-filled syringe of diluent. Patients will receive training and be provided with an instruction sheet with details, on how to store, prepare, self-administer and discard/keep used trial medication.

#### **9.7. Handling and Storage**

Presendin, the active trial medication, contains the active ingredient, exenatide, which is hygroscopic and light sensitive and must be protected from light during storage. Prior to use, all trial medication should be stored refrigerated at 2-8°C.

#### **9.8. Product Accountability and Assessment of Compliance**

In accordance with International Council of Harmonisation – Good Clinical Practice (ICH-GCP), each trial centre will account for all supplies of trial medication. Details of receipt, storage, assembly, and return will be recorded. The unit of accountability will be one single active or placebo vial. Needles will be disposed of in a sharps box.

All unused supplies will either be destroyed or returned to the trial Sponsor at the end of the trial in accordance with instruction by the Sponsor.

All trial medication will be self-administered by the patients. If a dose is not administered as planned, patients will record the missed dose in their electronic/paper diaries and it will be documented in the electronic case report form (eCRF).

Study Number: INVEX-CLIN-IIH-301 Protocol	Compound No.: Presendin
	Version: 5.0 for EU countries dated 08Dec2022

## 9.9. Treatment of Investigational Product Overdose

Definition of Overdose: More than 1 (one) dose in 24 hours.

In the event a patient overdoses on trial medication the Investigator should be notified as soon as possible. If symptoms appear, the Investigator will treat the patient according to their clinical judgement depending on the type of clinical signs and symptoms exhibited by the patient. The Sponsor should be notified in writing within 24 hours of the Investigator becoming aware.

Effects of overdose that may be seen include severe nausea, severe vomiting and rapidly declining blood glucose concentrations.

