Visit	SCREENING PERIOD 	RANDOMISED PERIOD 									FOLLOW UP	
	V1 Clinic	V2 Clinic Baseline	V3 TC	V4 Clinic	V5 Clinic	V6 Clinic	V7 Clinic	V8 Clinic	V9 Clinic	V10  Clinic		Unscheduled repeat visual assessments 
Visit Window (days)		+3	± 1	± 3	± 3	± 5	± 5	± 5	± 5	± 14		± 5
Month	0	0			1	2	3	4	5	6		
Week	-1	0		2	4	8	12	16	20	24		29
Day	-7	1	3	15	29	57	85	113	141	169		204
Pharmacokinetic (PK) sampling 		X 		X	X	X	X	X	X	X		
Anti-Drug Antibodies (ADA) sampling		X		X	X	X	X	X	X	X		
Lumbar Puncture 										X 		
Trial medication training 	X	X										
Randomisation		X										
Trial medication Dispensing	X	X			X	X	X	X	X			
Trial medication Accountability				X	X	X	X	X	X	X		

 The screening period must be a minimum of 7 days, up to a maximum of 10 days. Patients who do not meet the eligibility criteria based on diary review at randomisation/baseline (e.g., too few headache days or unacceptable concomitant medication use) will be considered screen failures; however, if the patient wishes and the Investigator is in agreement, he/she can be re-screened as a new patient. If the screening period exceeds 7 days, then eligibility will be based on the last 7 days of the screening period, i.e., the 7 days prior to randomisation visit. Trial site research team should review diaries remotely on a weekly basis to ensure compliance and follow up any patients with missing data

 Vital signs to include: blood pressure and heart rate

 Women of child-bearing potential. Serum pregnancy test to be conducted at screening, thereafter, highly sensitive urine pregnancy tests will be conducted. Visit 11 urine pregnancy test may be conducted at home

 Frisén grade will be evaluated locally and the presence of papilloedema verified by the OCT Reading Centre at screening to confirm eligibility. Indeterminate cases should be referred to the IAC (and supplemented with fundus photography and ultrasound scan of the optic nerve) to confirm papilloedema prior to randomisation visit

 Haematology, coagulation, biochemistry and urinalysis

 All actual sampling times and dosing times will be recorded

 Baseline Post-dose PK blood sample

Study Number: INVEX-CLIN-IIH-301 Protocol	Compound No.: Presendin
	Version: 5.0 for EU countries dated 08Dec2022

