#### **1.1.1. Name and Description of the Investigational Product**

Patients will receive active treatment, Presendin, or matching placebo.

Presendin is a modified release formulation of exenatide. Exenatide is a GLP-1 receptor agonist currently used in the management of type 2 diabetes. Presendin consists of a drug part (white or greyish white powder in a clear vial) and a diluent part (colourless liquid in a pre-filled syringe). The drug part is suspended in the diluent part solution and administered as a suspension. The patient or responsible person will be responsible for rehydrating the product for injection. Presendin is administered as a once weekly SC sustained-release injection containing 2.0 mg exenatide. Matching placebo will also be supplied as 2 parts, as visually identical vial and pre-filled syringe. The drug part will exclude the active pharmaceutical ingredient (exenatide acetate) and the diluent part will be the same as the active treatment diluent. Placebo is administered once weekly as a SC injection.

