## 12.2. Patient Withdrawal

### 12.2.1. Patient Withdrawal from Trial Treatment

A patient will be withdrawn from treatment for any of the following reasons:

- Withdrawal of consent to continue in the trial. The reason for this will be documented if provided
- The Investigator or Sponsor, for any reason, decides the patient should be withdrawn from the treatment
- Lack of compliance with the trial medication is classified as <75% or >125% of scheduled doses over the course of the trial, excluding supply issues
- Adverse events, which cannot be tolerated by the patient
- Pregnancy during the treatment period
- Retroactive failure to fulfil inclusion/ exclusion criteria (in this clinical drug trial designated phase III), if individual Benefit/Risk does not overrule
- New medical conditions not allowing for continuation of the protocol conform treatment
- Enrolment in any other clinical trial involving an investigational product, or enrolment in any other type of medical research judged not to be scientifically or medically compatible with this study
- If the patient, for any reason, requires treatment with another therapeutic agent that has been demonstrated to be effective for treatment of the study indication
- If the patient, for any reason, requires treatment with a concomitant medication that during this trial should be avoided for reasons of safety and/or efficacy reasons
- Any code breaking/unblinding requested by the investigator
- Protocol-mandated permanent discontinuation of the investigational study treatment

Patients will be encouraged to continue in the trial to the end of the randomised treatment period even if they stop trial medication so that data can be collected for the Intention-To-Treat (ITT) population.

If a patient is withdrawn from treatment during the randomised treatment period, they will be encouraged to return for all trial visits up to visit 10. If a patient does not want to return then at a minimum they should be encouraged to attend for visit 11 procedures as a safety follow-up visit.

Study Number: INVEX-CLIN-IIH-301 Protocol	Compound No.: Presendin
	Version: 5.0 for EU countries dated 08Dec2022

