### **13.4. Reporting Adverse Events**

All AEs and special reporting situations, whether serious or non-serious, will be reported from the time a signed and dated informed consent form is obtained until completion of the patient's final safety follow-up visit. The Sponsor will evaluate any safety information that is spontaneously reported by an Investigator beyond the time frame specified in the protocol. Adverse events reported after dosing will be classed as treatment emergent AEs.

All AEs, regardless of seriousness, severity, or presumed relationship to trial therapy, must be recorded using medical terminology in the source document and the eCRF. Whenever possible, diagnoses should be given when signs and symptoms are due to a common aetiology (e.g., cough, runny nose, sneezing, sore throat, and head congestion should be reported as "upper respiratory infection"). Investigators must record in the source documents and the eCRF their opinion concerning the relationship of the AE to trial therapy. All measures required for AE management must be recorded in the source document and reported according to Sponsor instructions. The patient must be provided, on the first day of trial medication (Day 1), with a "patient card" indicating the following:

- Patient number
- Name of the investigational product
- Investigator's name and 24-hour contact information
- Statement that the patient is participating in a clinical trial

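### The overdose definition uses a 24-hour window for a once-weekly sustained-release injection, so an extra dose later in the same week escapes the section 9.9 notifications

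*Protocol*

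**What the plan says.** Section 9.9 of the Protocol (version 5.0) gives the rule in one line: "Definition of Overdose: More than 1 (one) dose in 24 hours". Two duties hang on it. The Investigator is to be told as soon as possible, and the Sponsor is to receive written notice within 24 hours of the Investigator learning of the event. The section names severe nausea, severe vomiting and a rapid fall in blood glucose as possible effects. The version 4.0 text has the same definition.

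The product is described elsewhere:

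- Section 1.1.1: "Presendin is administered as a once weekly SC sustained-release injection containing 2.0 mg exenatide".
- Section 9.1.1: "Presendin (2.0mg exenatide) as a SC injection, self-administered once weekly".
- Section 9.2 puts the time to steady state for this formulation at 7 to 8 weeks.

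Other sections bear on extra doses:

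- Section 9.8, on the diary: "If a dose is not administered as planned, patients will record the missed dose in their electronic/paper diaries".
- Section 12.2.1, on compliance: "Lack of compliance with the trial medication is classified as <75% or >125% of scheduled doses over the course of the trial".
- Section 13.4, on safety reporting: "All AEs and special reporting situations, whether serious or non-serious, will be reported".
- Table 1, footnote 6: "All actual sampling times and dosing times will be recorded".
- Table 1 schedules medication accountability at visits 4 to 10, and its footnote 1 asks sites to review diaries remotely every week.

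**The concern.** The overdose window is one day and the dosing interval is seven. A one-day window would suit a product taken daily or more often. Here the obvious dosing error is a second injection some days early, and the definition leaves most such errors out.

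What is at stake is prompt safety reporting. All dosing is by the patients themselves, and from visit 5 medication is dispensed at visits nominally four weeks apart, so patients hold several doses at home. If an extra dose causes no symptoms, nothing in section 9.9 calls for anyone to be told, and the excess may first come to light at the next vial count. If it does cause symptoms, the adverse event is still reportable, but the overdose notice to the Sponsor is not required. The analysis of efficacy is not involved.

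**Working it through.** **Inputs.** Overdose window 24 h (9.9). Dosing interval 7 days, i.e. 7 × 24 = 168 h (9.1.1). Dose 2.0 mg (1.1.1). Over-compliance limit: above 125% of scheduled doses over the whole trial (12.2.1). Clinic days for visits 4 to 10: 15, 29, 57, 85, 113, 141, 169 (Table 1).

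**1. Share of the week outside the definition.**

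- Counting only from the previous dose: 168 − 24 = 144 h, and 144/168 = 86%.
- If the next scheduled dose is taken on time, an extra dose less than 24 h before it is also caught: 168 − 48 = 120 h, and 120/168 = 71%.

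**2. Amount injected.** One extra dose 48 h after the last gives 2 × 2 mg = 4 mg in that week against 2 mg planned. This is a two-fold injected amount. It is not an exposure ratio, which the protocol gives no means of computing.

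**3. Does the 125% rule act as a backstop?** The protocol does not state the number of scheduled doses. Weekly dosing for 24 weeks gives 24. A dose on the day of visit 10, or a delayed visit 10, could make it 25 or 26, so all three are shown.

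| Scheduled doses | One extra dose | Highest count that passes | First count above 125% |
|---|---|---|---|
| 24 | 25/24 = 104.2% | 30/24 = 125.0% | 31/24 = 129.2% |
| 25 | 26/25 = 104.0% | 31/25 = 124.0% | 32/25 = 128.0% |
| 26 | 27/26 = 103.8% | 32/26 = 123.1% | 33/26 = 126.9% |

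In each row six extra doses pass (30 − 24 = 31 − 25 = 32 − 26 = 6) and the seventh crosses the limit. A single extra dose is nowhere near it.

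**4. When would a vial count find it?** From visit 5 on the nominal gaps are 57 − 29 = 85 − 57 = 113 − 85 = 141 − 113 = 169 − 141 = 28 days. Earlier they are shorter: 29 − 15 = 14 days between visits 4 and 5.

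**5. Do the remaining controls restore the notifications?**

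- The diary is reviewed weekly, but section 9.8 asks patients to enter missed doses and does not mention extra ones.
- Dosing times are recorded, but no notification follows from that record.
- Section 13.4 covers special reporting situations without defining them. A site wanting to know what counts as an overdose would turn to section 9.9.

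None of these requires the contact or the written notice that section 9.9 provides.

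**The case against.** The best reply is that the window is a clinical choice. Section 9.9 concerns the treatment of overdose and lists acute effects, and a short window suits two injections given almost together. Whether doses two or more days apart also matter is a pharmacological question that the protocol does not quantify. Slow accumulation to steady state even suggests that one extra dose adds to several still contributing, so the rise in exposure could be well under two-fold. This stands as a limit on the claim: no size of harm follows from the document. It does not explain why a doubled weekly amount should go without notice, and the protocol offers no rationale for 24 hours.

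Second, detection may be better than the vial counts suggest. Diaries are reviewed weekly, dosing times are recorded, early counts are about 14 days apart, and the special-situations clause might cover a symptom-free extra dose. These controls are real and may shorten the delay, but none of them triggers the section 9.9 duties.

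Third, repeated extra dosing would need spare vials, and the protocol states no surplus supply. That is fair. The six-dose figure shows only how loose the 125% rule is as a backstop; it does not forecast behaviour. A single extra dose needs no surplus, since a later week's vial can be used early.

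Last, the patient instruction sheet and the Pharmacy Manual are not available and may set a minimum gap. Even so, the definition in the protocol would still need correcting to agree with them.

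**Conclusion.** The point holds and should be fixed. The definition in section 9.9 does not fit the dosing interval, and followed exactly it leaves an extra dose more than 24 hours from any other dose outside both notifications. That covers 71% to 86% of each week, depending on whether the next scheduled dose is taken on time. The 125% rule does not help with isolated extra doses, and this conclusion is the same for 24, 25 or 26 scheduled doses.

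The reach is narrow. Doses within 24 hours of each other are covered, and resulting adverse events are still reported. The conclusion rests on the text of the protocol alone and makes no claim about the exposure or harm that an extra dose within the week would cause.

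**What to change.** In section 9.9, define overdose by the weekly interval: more than one dose within the 7-day dosing interval, with a minimum gap below which the event counts. The sponsor's medical team should set that gap so that ordinary shifts of the injection day, such as dosing on day 6, are not flagged. In section 9.8, ask patients to enter extra doses in the diary as well as missed ones, so that the weekly diary review can find them. Add a matching line to the patient instruction sheet. The 125% rule in section 12.2.1 can stay, since it serves compliance.

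The cost is one definition, a few words in section 9.8 and a line in the patient materials. The downside is a few more overdose notifications to handle.

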## 9.10. Occupational Safety

There are no known occupational safety risks to staff. The Material Safety Data Sheet will be made available where required by local regulations.

## 10. TREATMENT FAILURE AND RESCUE THERAPY PROCEDURES

### 10.1. Treatment Failure

Rescue therapy can be initiated when there is a treatment failure. Since perimetric variability increases with increasing visual field damage, a two-tiered approach is used [[Wall, 2013](#)].

#### 10.1.1. Possible treatment failure

Possible treatment failure is defined as those with baseline PMD between -2 and -3.5dB who experience a decline of > or equal to 2dB. In those with a baseline PMD between -3.5 and -7 dB, those who experience a decline of > or equal to 3 dB.

When a possible treatment failure is identified, perimetry, and if needed, other visual tests, should be repeated at an unscheduled visit.

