- 8 The diagnostic LP will be the baseline LP and must be performed in lateral decubitus position. Patients with ICP <25 cm CSF at diagnosis will be excluded
- 9 Lumbar puncture to be performed after visual assessment. LP to be performed as per Appendix 1. CSF sample from visit 10 LP will be retained for future potential analysis
- 10 Patients will be provided with training on the self-administration of the trial medication. The patient will be asked to self-administer placebo at visit 1 to demonstrate ability to self-inject. Patients who are not comfortable to self-inject will be excluded
- 11 If patients discontinue in the randomised double-blind treatment period they will be encouraged to return for all trial visits up to visit 11. If a patient does not want to return for all visits then they will be asked to return at a minimum for visit 11 procedures for safety follow up
- 12 In the 4 weeks prior to visit 10, patients must not have missed more than one dose of trial medication and must have self-administered their final dose within 7 days of visit 10. Patients will be reminded by the trial site to self-administer trial medication weekly, to continue this until the completion of visit 10 and to bring their trial medication with them at visit 10 for return.  
Where more than one dose has been missed during the preceding 4 weeks, visit 10 should be delayed. Self-administration of trial medication should continue at 7-day intervals and then visit 10 rescheduled to ensure no more than one dose of the trial medication has been missed in the previous 4 weeks. Visit 10 should be delayed no more than 14 days
- 13 Optional unscheduled visit for visual testing (HVF, OCT, LogMAR) for patients in whom there is concern about visual decline or who perform inadequately or where there is technical failure (more than 15% false positive responses or inadequate performance indicated by the Visual Field Reading Centre for HVF; or OCT imaging not of satisfactory quality as determined by the OCT Reading Centre)
- 14 In the event of any abnormal safety assessments identified at end of treatment, e.g., abnormal ECG, abnormal routine laboratory results or ongoing adverse events, this visit may be performed at the clinic to repeat or follow up safety assessments
- 15 Reporting of AEs/SAEs will continue up to the final follow up visit 11

Study Number: INVEX-CLIN-IIH-301 Protocol	Compound No.: Presendin
	Version: 5.0 for EU countries dated 08Dec2022

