#### **6.1.7. Unscheduled visit for repeat visual assessments**

Optional unscheduled visit for visual testing (HVF, OCT, LogMAR) for patients where there is concern about their visual decline or who perform inadequately or where there is

Study Number: INVEX-CLIN-IIH-301 Protocol	Compound No.: Presendin
	Version: 5.0 for EU countries dated 08Dec2022

technical failure (more than 15% false positive responses or inadequate performance indicated by the Visual Field Reading Centre for HVF; or OCT imaging not of satisfactory quality as determined by the OCT Reading Centre). Imaging only in the study eye(s).

- Optical coherence tomography Imaging
  - Sites should initially check the scan quality. The OCT scan should go through the upload process to the OCT Reading Centre. The OCT scan will then be reviewed by the OCT Reading Centre for a full quality assessment. The report from the OCT Reading Centre will be sent to the site. Where the OCT is of insufficient quality it should be repeated as soon as possible at an unscheduled visit. Where the OCT processing is of insufficient quality it should be reprocessed as soon as possible by the site.
- Humphrey Visual Field (24-2 SITA-Standard)
  - Sites should initially check the performance quality of the HVF (to ensure no more than 15% false positives). The HVF should then be uploaded to the Visual Field Reading Centre without delay (an initial quality assessment takes place during the upload procedure). The HVF will then be reviewed by the Visual Field Reading Centre for a full quality assessment. Quality reports from the Visual Field Reading Centre will be received by the site. Where the visual field is of insufficient quality it should be repeated at an unscheduled visit without delay.
- Visual Acuity (LogMAR score)

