### **6.3.2. Visual Assessments**

Visual assessments should be performed on both eyes. All visual assessments should be uploaded without delay on the day of the visit to the OCT and Visual Field Reading Centres. In all cases the site is responsible for initial checks of the clinical data in the wider context of the patient’s disease, as well as a data quality check.

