#### 10.1.2. Definite treatment failure

A definite treatment failure occurs when a patient with baseline PMD between -2 and -3.5dB experiences a decline of > or equal to 2dB which remains after repeat perimetry.

Study Number: INVEX-CLIN-IIH-301 Protocol	Compound No.: Presendin
	Version: 5.0 for EU countries dated 08Dec2022

Or in those with a baseline PMD between -3.5 and -7 dB who experience a decline of > or equal to 3 dB which remains after repeat perimetry.

These cases should be reviewed without delay by the IAC (who will review all visual and clinical data) to confirm or refute a definite treatment failure.

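### Section 6.1.7 limits imaging at unscheduled visits to study eyes, against the both-eye OCT repeat rule at Visits 2 and 10 and the both-eye rule in 6.3.2

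*Protocol*

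**What the plan says.** All references are to Protocol Version 5.0 unless stated.

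- **Eligibility (5.2.1, criteria 5 and 6).** Papilloedema must be bilateral. A PMD of -2 to -7 dB is needed in at least one eye, and eyes in that range are the study eyes.
- **Unscheduled visit (6.1.7).** The visit is for patients where there is "concern about their visual decline", for inadequate performance, or for technical failure, which includes OCT of unsatisfactory quality. The description ends: "Imaging only in the study eye(s".
- **Same visit in Table 1, footnote 13.** It is offered "for patients in whom there is concern about visual decline" and for failed tests. Eyes are not mentioned.
- **General rule (6.3.2).** "Visual assessments should be performed on both eyes".
- **Visit 2 (6.1.2) and Visit 10 (6.1.5).** OCT is listed under assessments of both eyes, and a scan of insufficient quality is to be repeated promptly at an unscheduled visit.
- **Treatment failure (10.1.1, 10.1.2).** "Possible treatment failure is defined as those with baseline PMD between -2 and -3.5dB who experience a decline of > or equal to 2dB". For the worse band: "In those with a baseline PMD between -3.5 and -7 dB, those who experience a decline of > or equal to 3 dB". The definite-failure rule uses the same two bands, with the decline persisting on repeat perimetry. It is worded by patient ("A definite treatment failure occurs when a patient with baseline PMD between -2 and -3.5dB"), and "These cases should be reviewed without delay by the IAC".

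**The concern.** The unscheduled visit is where a worrying or failed visual test is followed up. If the eye that caused the worry is a swollen fellow eye outside the PMD range, 6.1.7 says not to image it at that visit. Other current text says that eye's inadequate scan should be repeated at just such a visit.

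What is at stake is patient safety and consistent practice between sites. Section 1.1 says patients are often unaware of field loss until it is more severe, so waiting for a complaint is a weak substitute for testing.

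The failure criteria raise a smaller question about the same eyes. They speak of a patient's baseline PMD and decline without naming an eye, so sites must infer which eye counts. The secondary endpoint of treatment failure refers to 10.1.1 for its criteria.

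**Working it through.** There is no plan figure to reproduce. The check sets the texts side by side and adds simple date arithmetic.

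**1. Can a swollen eye be a non-study eye?** Yes. Criterion 5 requires papilloedema in both eyes and criterion 6 requires the PMD range in only one. Vision exclusions 7 to 9 (5.2.2) are limited to study eyes. A fellow eye better than -2 dB or worse than -7 dB can therefore be enrolled. The protocol does not say how many patients will have a single study eye, so no count is possible.

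**2. Eye scope of each instruction.**

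- 6.1.7, unscheduled visit: imaging in study eyes only.
- 6.1.2 and 6.1.5, Visits 2 and 10: OCT in both eyes, with an inadequate scan repeated at an unscheduled visit.
- 6.3.2, all visual assessments: both eyes.
- Table 1 footnote 13, unscheduled visit: silent on eyes.

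**3. Apply them to one case.** Suppose a fellow-eye OCT at Visit 2 is inadequate. Section 6.1.2 sends it to an unscheduled visit for repeat. Section 6.1.7 then says that eye is not imaged there. The two cannot both be followed. The limit also covers a visit prompted by decline in the fellow eye, because decline is one of the stated purposes in 6.1.7.

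**4. What 6.1.7 does not bar.** "Imaging" most naturally means OCT, so repeat perimetry and acuity in the fellow eye remain open.

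**5. Length of the postponement.** The nominal days of the visits from baseline with scheduled OCT (Table 1) are 1, 15, 29, 57, 85, 113, 141 and 169. The gaps are:

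- 15 - 1 = 14 and 29 - 15 = 14
- 57 - 29 = 28, 85 - 57 = 28, 113 - 85 = 28, 141 - 113 = 28 and 169 - 141 = 28

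An unscheduled visit *d* days after a scheduled one leaves a wait of (gap - *d*) days to the next scheduled OCT. With *d* > 0 the wait is always shorter than the gap, so nominally under 28 days. Table 1 schedules no OCT after Visit 10, so this bound does not cover a failed scan at Visit 10 itself.

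**6. Failure criteria.** The bands in 10.1.1 and 10.1.2 run from -2 to -3.5 dB (decline of at least 2 dB) and from -3.5 to -7 dB (decline of at least 3 dB). Neither section says whether baseline and decline must come from the same eye, or which threshold applies when a patient has one study eye in each band. Section 14.2.1.1 (PMD power) enlists every eye that meets eligibility, so judging each study eye against its own baseline is the natural reading, but it is not written down.

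**The case against.** **6.1.7 may be a deliberate exception for an optional visit.** A specific sentence can override the general rule in 6.3.2, and PMD is analysed in eligible eyes. That answers 6.3.2 on its own. It does not answer Visits 2 and 10, which send both-eye scans to the same visit.

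**The bar is not absolute.** Section 6.3.2.2 asks for an inadequate OCT to be repeated as soon as possible with no eye limit. Section 10.1.1 allows other visual tests at the unscheduled visit, also with no eye limit. This stands: the defect is contradictory instruction, not proof that the fellow eye will go unscanned.

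**Judgement routes exist.** Both eyes are tested at scheduled visits. Site concern about OCT or visual field findings gets prioritised reading-centre review and, when indicated, expedited IAC review (6.3.2.2, 6.3.2.3). Rescue for progressive visual loss has no eye or dB limit (10.2). This stands and keeps the point minor. The IAC charter and the OCT and visual field procedures were not available and may give further guidance.

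Four stronger readings are tempting but not supported:

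- **A missing numeric trigger for fellow eyes is an error.** On a per-eye reading, an eye at -1.9 dB could fall 5 dB to -6.9 dB and meet no criterion. But 10.1.1 and 10.1.2 are written by patient and name no eye, so the gap depends on the reading chosen. Leaving such eyes to judgement is also defensible: exclusions 7 to 9 do not screen them, and 10.1 notes that perimetric variability rises with field damage.
- **Footnote 13 contradicts 6.1.7.** It is silent on eyes, and silence is not conflict.
- **OCT could be delayed by 38 or 47 days.** Those figures (28 + 5 + 5 and 28 + 5 + 14) are the widest gaps between scheduled visits within their windows, not waits from the unscheduled visit.
- **Trial results are affected.** Nothing here bears on the primary intracranial pressure analysis.

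**Conclusion.** The conflict between 6.1.7 and the both-eye OCT repeat rule at Visits 2 and 10 is real, and 6.3.2 points the same way. It is a minor safety and consistency defect. Followed literally, it postpones OCT of a fellow eye that prompted the visit to the next scheduled visit, less than one visit interval away and nominally up to 28 days. This assumes that "imaging" means OCT and that the site follows 6.1.7 rather than the texts with no eye limit. The number of patients affected cannot be stated.

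The silence of 10.1.1 and 10.1.2 on which eye governs is a secondary ambiguity to be cleared up in wording. Whether fellow eyes outside -2 to -7 dB should have a numeric trigger is a clinical choice for the sponsor and the IAC, not an error in the plan.

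**What to change.** - **6.1.7:** replace the study-eye imaging sentence with an instruction to repeat OCT, perimetry and acuity in any eye that prompted the visit, whether for decline or for a failed test. This agrees with Visits 2 and 10 and with 6.3.2, and needs no change to footnote 13.
- **10.1.1 and 10.1.2:** state that each study eye is judged against its own baseline and that either can qualify. Leave the 2 dB and 3 dB thresholds as they are.
- **Version 4.0**, bound in the same file, has the same wording in 6.1.7, 10.1.1.1 and 10.1.1.2. Make the same edits there if it is still in force.

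The cost is protocol wording plus, at some unscheduled visits already taking place, imaging of one more eye.
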